9.1.6 Weight and Height

Weight will be measured and recorded as noted in the Schedule of Events. For weight measurement, children should be weighed in clothes, with a dry diaper (if applicable), and no shoes. A standing height will be measured and recorded as noted in the Schedule of Events. Height and weight measurements for each subject should be performed using consistent and appropriately calibrated equipment (per institutional requirements) for each type of measurement across visits.

9.1.7 Vital Signs

Resting (minimum of 5 minutes) measurements of body temperature, blood pressure, pulse and respirations will be performed and recorded as noted in the Schedule of Events.

9.1.8 Oximetry

A resting (minimum of 5 minutes) measurement of oximetry will be measured on room air and recorded as noted in the Schedule of Events.

9.1.9 Spirometry

Spirometry will be performed as noted in the Schedule of Events study visits by participants 4 years of age and older at the time of randomization; who are able to reproducibly perform spirometry [31]. Spirometry will be performed in accordance with the current American Thoracic Society recommendations for the performance and interpretation of tests.

The same spirometry equipment should be used for the duration of the study whenever possible. Raw lung function measurements will be recorded. Percent of predicted measurements will be calculated centrally.

Bronchodilator use at each visit should be consistent throughout the study for reproducible results.

For subjects that routinely use bronchodilator reference the standard guidelines, as noted below:

- Subjects who routinely use short acting inhaled bronchodilators should use them 15 minutes to 2 hours prior to PFTs during study visits.
- Subjects who routinely use long acting bronchodilator agents should use them 15 minutes to 6 hours prior to PFTs during study visits.

If a bronchodilator is not used prior to spirometry at Visit 2 or Combined Visit 1 and Visit 2, subjects should not use a bronchodilator prior to spirometry at subsequent visits.

9.1.10 Subject Questionnaire

Parent/Guardian will complete a Cystic Fibrosis GI parent questionnaire at the beginning of each visit as noted in the Schedule of Events. This questionnaire includes 14 questions and takes less than five minutes to complete.

9.1.11 Subject Diary

Parent/Guardian will be requested to complete a daily diary to document each dose of study treatment from Visit 2 to Visit 4. The diary will be dispensed and reviewed as noted in the Schedule of Events.

9.1.12 Antibiotic Utilization Assessment

When a subject initiates a new IV, oral, or inhaled antibiotic, the presence of specific signs and symptoms will be assessed and documented. These data will be used to determine the incidence of a protocol defined PE based on the definition in Appendix 2.

9.1.13 Adverse Events

Information regarding occurrence of AE will be captured throughout each subject's study participation, starting after the first dose of study drug. Duration (start and end dates), grade, seriousness, outcome, treatment, and relation to study drug will be recorded on the case report form (CRF).

9.2 Clinical Laboratory Measurements

9.2.1 Hematology

Blood will be obtained as noted in the Schedule of Events and sent to each site's clinical hematology lab for a complete blood count (hemoglobin, hematocrit, red blood cell count, white blood cell count, white blood cell differential, and platelet count). If values are abnormal and clinically significant at Visit 4, a sample will be collected and these parameters re-evaluated at a follow-up visit two weeks later.

9.2.2 Blood Chemistry Profile

Blood will be obtained as noted in the Schedule of Events and sent to each site's clinical chemistry lab for determination of high-sensitivity C-reactive protein (hs-CRP), aspartate aminotransferase (AST/SGOT), alanine aminotransferase (ALT/SGPT), gamma-glutamyl transferase (GGT), and an electrolyte panel (sodium, potassium, chloride, bicarbonate) and renal function (BUN and creatinine). If values are abnormal and clinically significant (with an exception of hs-CRP) at Visit 4, a sample will be collected and these parameters re-evaluated at a follow-up visit two weeks later.

9.2.3 Spot Fecal Elastase

For subjects with no historical documentation of fecal elastase results, a spot fecal elastase test will be performed on the fecal specimen obtained at Visit 1 (or Combined Visit 1 and Visit 2) to document pancreatic insufficiency.

9.3 Research Laboratory Measurements

9.3.1 Blood Specimens for Metabolomics and REDOX Balance

Approximately four and half (4.5) mL of blood will be collected as noted in the Schedule of Events. The blood will be aliquoted/processed for plasma as detailed in the Study Lab Manual. All specimens will be labeled; two cryovials will be batch-shipped for analysis, while the other cryovial will be kept on site as a back-up. Required specimens will be batch-shipped frozen throughout the study to [name] Laboratory Emory University for analysis.

The specimens will be analyzed for:

- Plasma Redox assay: GSH, GSSH, cysteine, cystine, redox ratios and potential for the GSH and cysteine couples will be assessed.
- Plasma metabolomics assay: acylcarnitines, amino acids, biogenic amines, monosaccharides, sphingolipids and glycerophospholipids will be assessed

9.3.2. Fecal Calprotectin

Collection supplies and instructions will be provided for fecal collection at home as noted in the Schedule of Events. Subjects will be instructed to collect and freeze the samples at home and bring to the clinic at their next study visit. The sample will be stored frozen at -70 to -80°C at the site and batch shipped to the CFFT TDN Center for Biochemical Markers (CBM) located at Children's Hospital Colorado (Aurora, CO) for fecal calprotectin analysis.

9.3.3 Specimens for Long-Term Biorepository Storage

Instructions for specimen collection, processing, storage and shipping of samples will be provided in the Study Laboratory Manual.

For long-term biorepository storage, the following specimens will be collected from participating subjects who provide optional consent for the CFF Registry ID and for the CFFT biorepository as noted in the Schedule of Events:

- Plasma: Approximately 4.5 mL of blood will be collected.
- Fecal: a portion of fecal sample (collected per the instructions noted in Section 9.3.2 above) will be sent to the CFFT Biorepository for long-term storage.

The samples will be processed and stored frozen at -70 to -80°C at the site and batch shipped to the CFFT biorepository for long-term biorepository storage.

10 EVALUATIONS BY VISIT

10.1 Visit 1 (Day – 42 through– 1)

1. Review the study with the subject (subject's legal representative) and obtain written informed consent and HIPAA authorization and assent, if appropriate.
2. Review the optional consent for Specimen Banking (Subjects who elect not to provide biorepository specimens are still eligible for this study).
3. Review the "Consent for Collection and Use of your CFF Registry ID Number" and ensure that the subject (or subject's legal representative) has checked one of the two options (Subjects who elect not to provide this information are still eligible for this study).
4. Assign the subject a unique screening number.
5. Record demographics data and if consent obtained, the CFF Registry ID.
6. Record medical history, including a history of CF, diagnosis date, and prior CF treatments.
7. Record concomitant medications.
8. Perform a complete physical examination.
9. Measure and record height and weight.
10. Dispense site specific fecal elastase collection kit (*only for subjects without a historical fecal elastase test to document pancreatic insufficiency*).
11. Dispense study fecal collection kit.
12. Schedule subject for Visit 2 (within 41 days).

10.2 Visit 2 (Day 0)

It is suggested to have a pre-visit reminder call at least one day prior to the visit to remind subject of key visit information (e.g., date, time, and fecal sample collection).

Day of Visit:

1. Review all eligibility criteria to confirm subject's eligibility for participation.
2. Obtain subject-collected fecal sample:
 - TDN CBM laboratory testing (fecal calprotectin)
 - Long-term bio-repository storage, CFFT biorepository vendor (*only for subjects with signed optional consent for CFF Registry ID and biorepository*)
3. If applicable (*only for subjects without a historical fecal elastase test to document pancreatic insufficiency*), obtain the site specific fecal elastase kit dispensed at Visit 1 from the subject and send to the local laboratory for testing.
4. Administer Cystic Fibrosis GI parent questionnaire.
5. Record changes to concomitant medications. Perform an abbreviated physical examination.
6. Measure and record height and weight.

7. Obtain and record vital signs and oximetry.
8. Perform and record spirometry, if ≥ 4 years old at the time of randomization.
9. Collect blood for:
 - On-site clinical laboratory testing (Refer to section 9.2.1 and 9.2.2)
 - REDOX/Metabolomics testing
 - Long-term bio-repository storage, CFFT biorepository vendor (*only for subjects with signed optional consent for CFF Registry ID and biorepository*)
10. For eligible subjects, complete the appropriate data entry in Medidata Rave to complete the randomization. (Refer to Study Manual and CRF completion Guidelines)
11. Dispense fecal collection kit.
12. Dispense study drug and syrup.
13. Administer first dose of the study drug.
14. Instruct subjects/parents on study drug administration and provide written instructions.
15. Provide subject diary.
16. Schedule subject for Visit 3 (Day 84 ± 7 days).

10.3 Combined Visit 1 and Visit 2 (Day 0)

Visit 1 can be combined with Visit 2 if a fecal sample can be obtained prior to dosing.

1. Review the study with the subject (subject's legal representative) and obtain written informed consent and HIPAA authorization and assent, if appropriate.
2. Review the optional consent for Specimen Banking (Subjects who elect not to provide biorepository specimens are still eligible for this study).
3. Review the "Consent for Collection and Use of your CFF Registry ID Number" and ensure that the subject (or subject's legal representative) has checked one of the two options (Subjects who elect not to provide this information are still eligible for this study).
4. Assign the subject a unique screening number.
5. Record demographics data and if consent obtained, the CFF Registry ID.
6. Record medical history, including a history of CF, diagnosis date, and prior CF treatments.
7. Record concomitant medications.
8. Review all eligibility criteria to confirm subject's eligibility for participation.
9. Administer Cystic Fibrosis GI parent questionnaire.
10. Perform a complete physical examination.
11. Measure and record height and weight.
12. Obtain and record vital signs and oximetry.

13. Perform and record spirometry, if ≥ 4 years old at the time of randomization.
14. Obtain subject-collected fecal sample:
 - TDN CBM laboratory testing (fecal calprotectin)
 - Long-term bio-repository storage, CFFT biorepository vendor (*only for subjects with signed optional consent for CFF Registry ID and biorepository*)
15. If applicable (*only for subjects without a historical fecal elastase test to document pancreatic insufficiency*), obtain subject-collected fecal sample and send to the local laboratory for fecal elastase testing.
16. Collect blood for:
 - On-site clinical laboratory testing (Refer to section 9.2.1 and 9.2.2)
 - REDOX/Metabolomics testing
 - Long-term bio-repository storage (CFFT biorepository vendor) (*only for subjects with signed optional consent for CFF Registry ID and biorepository*)
17. For eligible subjects, complete the appropriate data entry in Medidata Rave to complete the randomization. (Refer to Study Manual and CRF Completion Guidelines)
18. Dispense fecal collection kit
19. Dispense study drug and syrup.
20. Administer first dose of the study drug.
21. Instruct subjects/parents on study drug administration and provide written instructions.
22. Provide subject diary.
23. Schedule subject for Visit 3 (Day 84 ± 7 days).

10.4 Phone Call Week 4 (Day 28 ± 7 days)

1. Record any AEs and changes to concomitant medications. If a new IV, oral or inhaled antibiotic was prescribed, ensure that the Antibiotic Utilization Assessment form was completed.
2. Review adherence to the study treatment.

10.5 Phone Call Week 8 (Day 56 ± 7 days)

3. Record any AEs and changes to concomitant medications. If a new IV, oral or inhaled antibiotic was prescribed, ensure that the Antibiotic Utilization Assessment form was completed.
4. Review adherence to the study treatment.
5. Remind the parent/legal guardian to retain empty/or unused drug containers and bring them along with the diary to Visit 3.

10.6 Visit 3 (Day 84 ± 7 days)

It is suggested to have a pre-visit reminder call at least one day prior to the visit to remind subject of key visit information (e.g., date, time, fecal sample collection, bring all used and unused study drug bottles and diary to visit).

Day of Visit:

1. Administer Cystic Fibrosis GI parent questionnaire.
2. Perform adverse event review.
3. Record changes to concomitant medications. If a new IV, oral or inhaled antibiotic was prescribed, ensure that the Antibiotic Utilization Assessment form was completed.
4. Perform an abbreviated physical examination.
5. Measure and record height and weight.
6. Obtain and record vital signs and oximetry.
7. Perform and record spirometry, if ≥ 4 years old at the time of randomization.
8. Obtain subject-collected fecal sample for:
 - TDN CBM laboratory testing (fecal calprotectin)
 - Long-term bio-repository storage, CFFT biorepository vendor (*only for subjects with signed optional consent for CFF Registry ID and biorepository*)
9. Review subject diary.
10. Collect returned study drug containers.
11. Dispense fecal collection kit.
12. Dispense study drug and syrup.
13. Provide subject diary.
14. Schedule subject for Visit 4 (Day 168 ± 14 days).

10.7 Phone Call Week 16 (Day 112 ± 7 days)

1. Record any AEs and changes to concomitant medications. If a new IV, oral or inhaled antibiotic was prescribed, ensure that the Antibiotic Utilization Assessment form was completed.
2. Review adherence to the study treatment.

10.8 Phone Call Week 20 (Day 140 ± 7 days)

1. Record any AEs and changes to concomitant medications. If a new IV, oral or inhaled antibiotic was prescribed, ensure that the Antibiotic Utilization Assessment form was completed.
2. Review adherence to the study treatment.

3. Remind the parent/legal guardian to retain empty/or unused drug containers and bring them along with the diary to Visit 4.

10.9 Visit 4 (Day 168 ± 14 days)

It is suggested to have a pre-visit reminder call at least one day prior to the visit to remind subject of key visit information (e.g., date, time, fecal sample collection, bring all used and unused study drug bottles and diary to visit).

Day of Visit:

1. Administer Cystic Fibrosis GI parent questionnaire.
2. Perform adverse event review.
3. Record changes to concomitant medications. If a new IV, oral or inhaled antibiotic was prescribed, ensure that the Antibiotic Utilization Assessment form was completed.
4. Perform an abbreviated physical examination.
5. Measure and record height and weight.
6. Obtain and record vital signs and oximetry.
7. Perform and record spirometry, if ≥ 4 years old at the time of randomization.
8. Obtain subject-collected fecal sample for:
 - TDN CBM laboratory testing (fecal calprotectin)
 - Long-term bio-repository storage, CFFT biorepository vendor (*only for subjects with signed optional consent for CFF Registry ID and biorepository*)
9. Collect blood for:
 - On-site clinical laboratory testing (Refer to section 9.2.1 and 9.2.2)
 - REDOX/Metabolomics testing
 - Long-term bio-repository storage, CFFT biorepository vendor (*only for subjects with signed optional consent for CFF Registry ID and biorepository*)
10. Review subject diary.
11. Collect and count returned study drug containers.
12. Schedule subject for Follow up Phone Call *or* Visit 5 (Day 182 ± 14 days).

10.10 Follow-Up Phone Call or Visit 5 (Day 182 ± 14 days)

For subjects with normal or abnormal, non-clinically significant lab values at Visit 4 and no on-going treatment-related AEs, call the subject's legal guardian and:

1. Review AEs and changes in concomitant medications with the subject.
2. Record in CRF.

For subjects with on-going treatment related AEs at Visit 4, have the subject return to the clinic for a follow-up visit.

1. Review AEs and changes in concomitant medications with the subject.
2. Record in CRF.

For subjects with abnormal, clinically significant clinical lab values at Visit 4, have the subject return to the clinic for a follow-up visit.

1. Record any AEs.
2. Record changes to concomitant medications.
3. Collect blood for laboratory tests that were abnormal and clinically significant at Visit 4 (e.g., Refer to section 9.2.1 and 9.2.2).

10.11 Early Permanent Discontinuation of Study Treatment Visit

1. Administer Cystic Fibrosis GI parent questionnaire.
2. Perform AEs review.
3. Record changes to concomitant medications. If a new IV, oral or inhaled antibiotic was prescribed, ensure that the Antibiotic Utilization Assessment form was completed.
4. Perform an abbreviated physical examination.
5. Measure and record height and weight.
6. Obtain and record vital signs and oximetry.
7. Perform and record spirometry, if ≥ 4 years old at the time of randomization.
8. Obtain subject-collected fecal sample (if available) for:
 - TDN CBM laboratory testing (fecal calprotectin)
 - Long-term bio-repository storage, CFFT biorepository vendor (***only for subjects with signed optional consent for CFF Registry ID and biorepository***)
9. Collect blood for:
 - On-site clinical laboratory testing (Refer to section 9.2.1 and 9.2.2)
 - REDOX/Metabolomics testing
 - Long-term bio-repository storage, CFFT biorepository vendor (***only for subjects with signed optional consent for CFF Registry ID and biorepository***)
10. Review subject diary.
11. Collect and count returned study drug containers.
12. Encourage the subject to return for any remaining study visits.

11 ADVERSE EXPERIENCE REPORTING AND DOCUMENTATION

11.1 Adverse Events (AE)

An AE is any untoward medical occurrence in a clinical investigation of a patient administered a pharmaceutical product and that does not necessarily have a causal relationship with the treatment. An AE is therefore any unfavorable and unintended sign (including an abnormal laboratory finding), symptom or disease temporally associated with the administration of an investigational product, whether or not related to that investigational product. An unexpected AE is one of a type not identified in nature, severity, or frequency in the current Investigator's Brochure or of greater severity or frequency than expected based on the information in the Investigator's Brochure.

The Investigator will probe, via discussion with the subject, for the occurrence of AEs during each subject visit and record the information in the site's source documents. AEs will be recorded in the subject CRF.

AE Severity

The National Cancer Institute's Common Terminology Criteria for Adverse Events (CTCAE) Version 4.0, as modified for cystic fibrosis, should be used to assess and grade AE severity, including laboratory abnormalities judged to be clinically significant. The modified criteria can be found in the Study Reference Binder. If the experience is not covered in the modified criteria, the guidelines shown in Table 2 below should be used to grade severity. It should be pointed out that the term "severe" is a measure of intensity and that a severe AE is not necessarily serious.

Table 2. AE Severity Grading

Severity (Toxicity Grade)	Description
Mild (1)	Mild; asymptomatic or mild symptoms; clinical or diagnostic observations only; intervention not indicated
Moderate (2)	Moderate; minimal, local or noninvasive intervention indicated; limiting age-appropriate Instrumental activities of daily living (e.g., preparing meals, using the telephone, managing money)
Severe (3)	Severe or medically significant but not immediately life-threatening; hospitalization or prolongation of hospitalization indicated; disabling; limiting self-care activities of daily living (e.g., bathing, dressing, feeding self, using toilet, taking medications)
Life-threatening (4)	Life-threatening consequences; urgent intervention indicated
Death (5)	Death related to AE

AE Relationship to Study Drug

The relationship of an AE to the study drug should be assessed using the following the guidelines in Table 3.

Table 3. AE Relationship to Study Drug

Relationship to Drug	Comment
Definitely	Previously known toxicity of agent; or an event that follows a reasonable temporal sequence from administration of the drug; that follows a known or expected response pattern to the suspected drug; that is confirmed by stopping or reducing the dosage of the drug; and that is not explained by any other reasonable hypothesis.
Probably	An event that follows a reasonable temporal sequence from administration of the drug; that follows a known or expected response pattern to the suspected drug; that is confirmed by stopping or reducing the dosage of the drug; and that is unlikely to be explained by the known characteristics of the subject's clinical state or by other interventions.
Possibly	An event that follows a reasonable temporal sequence from administration of the drug; that follows a known or expected response pattern to that suspected drug; but that could readily have been produced by a number of other factors.
Unrelated	An event that can be determined with certainty to have no relationship to the study drug.

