1.1 Overview of Non-Clinical Studies

Non-clinical studies of GSH have not been performed as the GSH formulation to be used in this study is considered a dietary supplement.

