8.2 Blinding

Study treatments will be administered in a double-blind fashion (i.e., subjects and site research staff will not know the treatment assigned, with the exception of the dispensing site pharmacist). The central pharmacy, designated TDNCC personnel responsible for creating drug assignment lists, and those involved in DMC report generation in accordance with the DMC Charter will be unblinded.

The following study procedures will be in place to ensure double-blind administration of study treatments:

- Randomization assignments will be stored in a secure database and appropriately protected and backed up
- Access to the randomization code will be strictly controlled and limited to designated TDNCC personnel who are involved in the generation of the interim report for the Data Safety Monitoring Board (DSMB)
- GSH and control treatments will be identical in appearance and taste masked with syrup prior to dosing.
- All dispensed GSH and control treatment bottle packaging and labeling will be identical.

During the study, the blind may be broken for individual subjects in emergencies when knowledge of the subject's treatment group is necessary for further patient management or when the event meets the Food and Drug Administration (FDA) expedited reporting requirements as a suspected adverse reaction that is serious and unexpected (US Code of Federal Regulations (CFR) 21 CFR 312.32(c)(1)(i)). In those cases, knowledge of the treatment received is necessary for interpreting the event. If the blind is broken and the subject was receiving placebo, an IND Safety Report would not be submitted. However, if the blind is broken and the subject is on

study drug, an IND Safety Report is submitted to the FDA and all participating investigators would be notified. Emergency un-blinding procedures are provided in the Study Manual (refer to the section on Serious Adverse Experience reporting).

The study blind will be broken on completion of the clinical study and after the study database has been locked and study results released. The site investigators will be provided with each subject's treatment assignment following completion of the statistical report and dissemination of top line results to Sponsor-Investigators.

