8.5 Dose Modification

Not Applicable

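### The causality table in Protocol 11.1 builds expectedness into relatedness, so a plausibly timed event of a new type and uncertain cause fits none of its four levels

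*Protocol*

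**What the plan says.** Section 11.1 gives the only causality scale in the two documents and presents it as guidance: "The relationship of an AE to the study drug should be assessed using the following the guidelines in Table 3". The table has four levels.

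- **Definitely** has two routes. One is an already recognised toxicity. The other combines plausible timing, a known or expected pattern, confirmation when the drug is stopped or reduced, and no other reasonable explanation. The entry begins "Previously known toxicity of agent; or an event that follows a reasonable temporal sequence from administration of the drug".
- **Probably** needs plausible timing, a known or expected pattern, confirmation on stopping or reducing, and other explanations being unlikely.
- **Possibly** needs plausible timing and an event "that follows a known or expected response pattern to that suspected drug; but that could readily have been produced by a number of other factors".
- The entry for **Unrelated** is "An event that can be determined with certainty to have no relationship to the study drug".

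There is no unlikely, unknown or not-assessable level.

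Three other parts of the protocol bear on this. Earlier in 11.1, an unexpected event is defined separately, by comparison with the Investigator's Brochure for nature, severity or frequency. Section 8.2 allows unblinding when an event meets the "expedited reporting requirements as a suspected adverse reaction that is serious and unexpected", with an IND safety report if the child was on active drug. Section 10.10 says: "For subjects with on-going treatment related AEs at Visit 4, have the subject return to the clinic for a follow-up visit". Section 4.1 and footnote b of Appendix 1 repeat that trigger. Section 9.1.13 has relation to study drug recorded on the case report form for adverse events.

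**The concern.** Relatedness and expectedness are different questions: whether the drug may have caused the event, and whether such an event had been described before. Table 3 makes a yes to the second a condition for a yes to the first. Section 8.2 needs the opposite combination, a yes to the first and a no to the second.

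The prior knowledge that would define a known pattern is thin. Section 1.1 states that "Non-clinical studies of GSH have not been performed". Section 1.2 describes two earlier CF studies, one that randomised 44 children and one that observed 13 patients. Section 2.1 expects related events to be mainly gastrointestinal and mentions rare reports of flatulence and hypersensitivity, including rash.

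At stake is consistent classification. Two sites seeing the same new event could record it differently and both depart from the table. One would stretch Possibly to an event with no known pattern, and the other would record Unrelated without the required certainty. The second choice could affect whether a reaction is treated as suspected under 8.2, and whether the child is seen in person at Visit 5.

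**Working it through.** The plan gives no figure to reproduce here. The check applies the table's wording literally to every kind of event.

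**Step 1. Inputs, from Table 3 of Section 11.1.** Describe an event by:

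- timing plausible or not (2 options);
- pattern known or expected, or not (2 options);
- confirmed on stopping or reducing, or not (2 options);
- other explanation: none, unlikely, or readily available (3 options).

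Assume throughout that the event is not certain to be unrelated, so Unrelated is closed. For each setting of the pattern there are 2 × 2 × 3 = 12 profiles.

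**Step 2. No known or expected pattern.** Possibly, Probably and the second route to Definitely each fail on the pattern condition. The first route to Definitely fails because the toxicity is not already known. So 12 of 12 profiles fit no level. Of these, 2 × 3 = 6 have plausible timing, and 3 of those 6 are confirmed when the drug is stopped or reduced. Even an event that resolves on stopping, with no other explanation, has no level if it is of a new type.

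**Step 3. Known or expected pattern with plausible timing, for comparison.** Setting aside the known-toxicity route to Definitely, 4 of 6 profiles fit a level. The other 2 are not confirmed on stopping or reducing and have no other explanation or only an unlikely one. The known-toxicity route would classify those 2 if it applied. The main gap is therefore the one in Step 2.

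**Step 4. Set the sections side by side.**

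| Section | What it needs |
|---|---|
| 8.2 | An event that is suspected and also unexpected |
| 11.1, definition of unexpected | Judged against the Brochure, apart from cause |
| 11.1, Table 3 | A related level only with prior knowledge of the toxicity or pattern |
| 4.1, 10.10, Appendix 1 footnote b | A treatment-related event, with no statement of which levels qualify |

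For an event unexpected in nature, rows 1 and 3 cannot both be met if the table's related levels are what make an event suspected.

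**Step 5. What a mis-scored event would miss.** Under 10.10, the visit for an ongoing related event and the telephone call have the same two steps: review adverse events and concomitant medications, then record them. The loss is the in-person setting, not the review. For a serious event, 11.2.1 sends the report to the coordinating center within one business day whether or not it is related. What may fail is its classification as suspected.

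**The case against.** The case against is strong on consequences, and most of it stands.

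- **Serious events are not lost.** They are reported regardless of cause (11.2.1), and medical monitors follow them throughout (Synopsis, planned interim analysis).
- **The link to 8.2 is inferred.** Section 8.2 cites the federal regulation and does not mention Table 3 or the site's score. Part of the protocol text following 11.2.1 was not available for this review, so a separate sponsor causality assessment cannot be excluded.
- **Visit 5 has its own safeguards.** Clinically significant abnormal laboratory results bring the child back whatever the cause, with hs-CRP excepted from the repeat testing. The other children get the call.
- **Scope is narrower than all unexpected events.** An event unexpected only in severity or frequency may still follow a known pattern and fit the table.
- **The table is offered as guidelines,** so an investigator may still choose Possibly. The wording does not support that choice, however, and sites may differ.

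A reader might infer more than the documents support, in four ways.

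1. *That a mis-scored event would vanish from the safety evidence.* The summaries in Protocol 15.5 and SAP 3.5, and the monitoring reports in SAP 1.2, cover adverse events by treatment group, and none is described as restricted to related events.
2. *That confirmation on stopping or reducing is impossible because Section 8.5 reads "Not Applicable".* The table accepts stopping alone, and 8.5.1 and 12.1 allow temporary and permanent discontinuation.
3. *That a fall in neutrophils at Visit 4 would miss Visit 5.* If clinically significant, it triggers the visit without any causality score.
4. *That the chance of seeing a rare reaction among the children on active drug measures the harm.* That figure is the chance that a reaction occurs under an assumed incidence. It is not the chance that the reaction is misclassified or lost.

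None of this closes the gap in the table. The safeguards act downstream of a scale that cannot classify the event.

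**Conclusion.** The point holds as a defect in the causality scale. Read literally, 0 of 4 levels fit a plausibly timed event that is new in nature and of uncertain cause, and the scale does not fit with the separate definition of unexpected in 11.1 or with the trigger in 8.2. The practical effect is limited to inconsistent site scoring, possible omission from the suspected class, and possible loss of an in-person Visit 5 for a non-laboratory event. It does not affect the primary endpoint, the sample size, the error rate or the planned adverse event tables.

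This rests on three assumptions: sites apply the table as written; relatedness for 8.2 and Visit 5 is taken from it, since the documents offer no other definition; and no unseen text, such as the Brochure, the study manual or the unavailable part of the protocol, supplies a different rule. How many events would be affected cannot be estimated from the documents.

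**What to change.** Reconcile Sections 8.2 and 11.1 and the Visit 5 wording through four changes.

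1. In Table 3, make a known or expected pattern supporting evidence for a related level rather than a necessary condition.
2. Make the levels cover every event, for example by replacing the certainty requirement for Unrelated or by adding an Unlikely level.
3. State that expectedness is judged separately from relatedness, using the definition already in 11.1.
4. Name the levels that count as treatment-related in 4.1, 10.10 and Appendix 1, and those that count as suspected in 8.2.

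The cost is a revised table, a changed pick-list on the case report form and matching completion guidance. The analyses in the SAP need no change. The downside is small: a few more events scored as possibly related, with some extra Visit 5 returns and expedited reviews.
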